4.2 Subgroups

The primary and secondary endpoints for the nonopioid cohort will be analyzed in the following subgroups:

- concomitant oral migraine preventive treatment initiated before screening and taken during baseline (Yes or No)
- geographic region (North America vs. Other)
- BMI (< median vs. ≥ median)
- prior history of treatment with onabotulinumtoxinA (Yes or No)
- total number of prior treatment failures (1 vs. 2 or more)
- total number of prior treatment failures (1 vs. 2 vs. 3 or more)
- **prior history of depression (Yes or No)**
- acute headache medication overuse category
 - overuse of triptan (Yes or No)
 - overuse of simple analgesics/NSAIDs (Yes or No)
 - overuse of combination analgesics (Yes or No)
 - overuse of combination therapies (Yes or No)

Summary of prior and concomitant migraine preventive medication use is based on the following 9 categories: topiramate, other antiepileptics, beta blockers, tricyclic antidepressants, other antidepressants, calcium channel blockers/calcium antagonists, angiotensin receptor blockers/angiotensin-converting enzyme (ACE) inhibitors, botulinum toxin, and other drugs used for migraine prevention.

5. Definitions

5.1 Definition of Terms Included in Study Endpoints

5.1.1 Efficacy Endpoints Based on Daily eDiary Collection

Acute Headache Medication (AHM)

Acute headache medications include

- Triptan-based migraine medications
- Ergotamine-based migraine medications
- **Ditan-based migraine medications**
- Non-opioid acute headache medications
- Non-opioid butalbital containing medications
- Opioid-containing acute headache medications
- Opioid-containing butalbital containing medications

Acute Migraine-specific Medication (AMSM)

A subset of acute headache medication consisting of triptan-based migraine medications, ergotamine-based migraine medications, **and ditan-based migraine medications.**

Medication Overuse (MO)

Monthly acute **headache** medication **use** meeting at least one of the following criteria:

- ≥ 10 days of a combination of ergotamines, triptans, opiates or opioid-containing meds or opioid combination-analgesic, non-opioid combination-analgesic medications or simple analgesics/NSAIDs **whilst not satisfying medication overuse criteria in any of the below individual medication categories alone**
- ≥ 10 days of opiates or opioid-containing medications or opioid combination-analgesics
- ≥ 10 days of triptans or triptan-containing medications
- ≥ 10 days of ergotamines or ergotamine-containing medications
- ≥ 10 days of non-opioid combination-analgesics

- ≥ 15 days of simple analgesics/NSAIDs if subjects use simple analgesics/NSAIDs **ONLY** during the monthly interval

Monthly acute headache medication days for each medication category will be calculated using the same proration approach as monthly acute headache medication days.

Concomitant migraine preventive medication

Migraine preventive medication that were reported in concomitant medication CRF, belonged to medication category defined in Section 4.2 and had start date < study day 1 AND (end date > day 1 OR missing end date).

Overuse of Combination Analgesics

Monthly acute headache medication days meeting at least one of the following criteria:

- ≥ 10 days of opioid-containing combination-analgesics
- ≥ 10 days of non-opioid combination-analgesics

Medication Overuse Headache (MOH; Over 3 Months)

Mean monthly AHMD ≥ 10 days AND mean MHD ≥ 14 days over 3 consecutive study months, **excluding gepant-based medication in the derivation.**

Absence of MOH (Over 3 Months)

Mean monthly AHMD < 10 days OR mean MHD < 14 days over 3 consecutive study months, **excluding gepant-based medication in the derivation.**

Sustained MOH Remission (Over 6 Months During DBTP)

Mean monthly AHMD < 10 days OR mean MHD < 14 days over 3 consecutive study months **at both time points** (months 1, 2, and 3 [week 1 to week 12], AND months 4, 5, and 6 [week 13 through 24]), **excluding gepant-based medication in the derivation.**

Absence of MOH at End of Study

Mean monthly AHMD < 10 days OR mean MHD < 14 days over months 11, 12 and 13 (week 41 through 52), **excluding gepant-based medication in the derivation.**

Sustained Absence of MOH (Sustained MOH Remission) Over 1 Year

Absence of MOH over the DBTP (months 1, 2, and 3 [week 1 through 12], OR months 4, 5, and 6 [week 13 through 24]) AND OLTP (months 11,12 and 13 [week 41 through 52]), **excluding gepant-based medication in the derivation.**

Conversion to Episodic Migraine (EM) (Over 3 Months)

Mean MHD < 14 days over 3 consecutive study months

Achievement of Conversion to Episodic Migraine (EM) (Over 6 Months During DBTP)

Mean MHD <14 days over months 1 through 6 (week 1 through 24) of the DBTP.

Qualified Headache

A qualified headache is defined as

- A headache of duration ≥ 4 hours, or
- A headache of duration < 4 hours during which an acute headache medication is administered

Headache Day

A calendar day (00:00 to 23:59) in which the subject experiences ≥ 1 qualified headache or takes ≥ 1 acute migraine-specific medication (ie, triptan, ergotamine, **ditan**) during aura

Qualified Migraine Headache

A qualified migraine headache is defined as

- A headache lasting for ≥ 4 hours, and meeting ≥ 1 of the following criteria (a and/or b):
 - a) ≥ 2 of the following pain features:
 - Unilateral
 - Throbbing
 - Moderate to severe (ie, headache pain intensity ≥ 4)
 - Exacerbated with exercise/physical activity
 - b) ≥ 1 of the following associated symptoms:
 - Nausea
 - Vomiting
 - Photophobia and phonophobia
- A headache during which an acute migraine-specific medication (ie, triptan, ergotamine, **ditan**) is administered regardless of the headache duration, pain features, and associated symptoms

Migraine Day

A calendar day (00:00 to 23:59) in which the subject experiences ≥ 1 qualified migraine headache or takes ≥ 1 acute migraine-specific medication (ie, triptan, ergotamine, **ditan**) during aura.

Migraine-free Day

A calendar day (00:00 to 23:59) **of a diary day** in which the subject does not experience any headache pain or any symptoms including aura, nausea, vomiting, phonophobia, and photophobia, and does not take any acute headache medication.

Acute Headache Medication Day

A calendar day (00:00 to 23:59) in which the subject takes ≥ 1 acute headache medication.

Opioid Medication Day

A calendar day (00:00 to 23:59) in which an opioid/opioid containing medication was administered.

Headache Pain Intensity

Worst or peak pain intensity collected on a headache ranges from 1 to 10 with a higher score indicating more severe pain. Pain intensity are categorized into mild (1 to 3), moderate (4 to 6), and severe (7 to 10).

Headache Day of at Least Moderate Pain Intensity

A calendar day (00:00 to 23:59) in which the subject experiences ≥ 1 qualified headache with the worse or peak pain intensity of ≥ 4 .

Diary Day

A calendar day (00:00 to 23:59) with complete headache, aura, and acute headache medication data recorded in the eDiary device.

Monthly Frequency Variable in Days

Number of days of interest during one monthly interval as defined in [Table 5-1](#). Monthly frequency variables include:

- Monthly migraine days (MMD)
- Monthly headache days (MHD)
- Monthly migraine-free days
- Monthly opioid/opioid-containing medication days
- Monthly acute headache medication days (AHMD)
- Monthly headache days with at least moderate pain intensity
- Monthly acute migraine-specific medication days

The following proration rule will be applied to all monthly frequency variables for analysis. If a subject misses diary on a day when a headache is ongoing, that day will still be included in MHD calculation as only headache duration is required to identify a

headache day. For other endpoints which are derived using headache symptoms and medication information, days without diary completion will not be included in the proration.

Within Each Monthly Interval	Monthly Frequency Variable
≥ 14 diary days	
For monthly headache days with at least moderate pain intensity, prorate to 28-day equivalent without rounding
 $\frac{\text{Number of observed headache days with at least moderate pain within each monthly interval}}{\text{Number of diary days or days with headache pain intensity collected within each monthly interval}} \times 28$
	
For monthly migraine-free days, prorate to 28-day equivalent without rounding
 $\frac{\text{Number of frequency days within each monthly interval}}{\text{Number of diary days or headache days or acute headache medication days within each monthly interval}} \times 28$
	
For monthly acute migraine-specific medication days and monthly opioid/opioid-containing medication days, prorate to 28-day equivalent without rounding
 $\frac{\text{Number of frequency days within each monthly interval}}{\text{Number of diary days or acute headache medication days within each monthly interval}} \times 28$
	
For other frequency variables, prorate to 28-day equivalent without rounding
 $\frac{\text{Number of frequency days within each monthly interval}}{\text{Number of diary days or frequency days within each monthly interval}} \times 28$ 
Note: diary days with complete headache, aura, and acute headache medication data is required to derive endpoints related to symptoms, pain intensity and acute medication use.

< 14 diary days	Set to missing

Monthly Average Variable Based on Qualified Headaches

Monthly average headache pain intensity based on qualified headache will be calculated as below:

Within Each Monthly Interval	Monthly Average Variable
≥ 14 diary days	Sum of the headache pain intensity values from all qualified headaches during a monthly interval as defined in Table 5-1 divided by the total number of qualified headaches in that monthly interval
	Set to 0 if no qualified headache reported
< 14 diary days	Set to missing

A headache lasts for multiple days will be separated to multiple qualified headaches by midnight. Multiple qualified headaches within the same day will be calculated as separate qualified headaches.

Monthly Average Variable Based on Daily PRO Scores

Monthly average variables derived from daily MPFID assessment include

- Monthly average physical impairment domain score
- Monthly average impact on everyday activities domain score

Days With Complete Response Within Each Monthly Interval	Monthly Average Variable
≥ 14 days	Sum of values from daily assessment during a monthly interval as defined in Table 5-1 divided by the number of days with complete response.
< 14 days	Set to missing

Complete response is defined as the completion of a MPFID questionnaire with all questions answered. The latest record of the duplicate MPFIDs will be used for the calculation of monthly MPFIDs.

Migraine Physical Function Impact Domains and Everyday Activities

The MPFID is a self-administered 13-item instrument measuring physical functioning. It has 2 domains, Impact on Everyday Activities (7 items) and Physical Impairment (5 items), and 1 stand-alone global question which provides an assessment of overall impact on everyday activities.

Subjects respond to items using a 5-point scale, with difficulty items ranging from "Without any difficulty" to "Unable to do" and frequency items ranging from "None of the time" to "All of the time". These are assigned scores from 1 to 5, with 5 representing the greatest burden. For each domain, the scores will be calculated as the sum of the item responses and the sum will be rescaled to a 0 to 100 scale, with higher scores representing greater impact of migraine (ie, higher burden). There will be a score for

each of the 2 domains and a third score for the stand-alone item. The recall period is the past 24 hours. Subjects will complete the MPFID daily using the eDiary.

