Statistical Analysis Plan

Protocol Title:	A Phase 4, Randomized, Double-blind, Placebo-controlled, Parallel-group Study to Evaluate the Efficacy and Safety of Erenumab in Adults With Chronic Migraine and Medication Overuse Headache	
Short Protocol Title:	A Phase 4 Randomized Controlled Study to Evaluate the Efficacy and Safety of Erenumab in Adults With Medication Overuse Headache	
Protocol Number:	20170703	
NCT Number:	NCT03971071	
Authors:	[REDACTED]	
Sponsor:	Amgen Inc. [name]	
SAP Date:	Document Version	Date
	Original (v1.0)	13 January 2020
	Amendment 1 (v2.0)	10 December 2022

Version Number	Date (DDMMYYYY)	Summary of Changes, including rationale for changes
Original (v1.0)	13JAN2020	NA
Amendment 1 (v2.0)	10DEC2022	
 • Section 4.2 updated to 
 ○ Include an additional subgroup analysis by prior history of depression ○ Clarify the medication categories of migraine preventive medications • Section 5.1 updated to 
 ○ Include ditans as acute migraine-specific medications and acute headache medication ○ Include the definition of concomitant migraine preventive medication ○ Clarify the exclusion of gepant-based medication in the derivation of MOH ○ Remove the definition of information day ○ Clarify the table of prorations of monthly frequency variable in days ○ Include the definition of treatment-related treatment-emergent adverse events ○ Clarify the calculation of a headache last for multiple days and multiple qualified headaches within the same day ○ Clarify the definition of complete response of MPFID • Section 5.2 updated to include the definition of primary completion date • Section 5.3 updated to 
 ○ Clarify the handling of measurements with multiple individual items ○ Include the definition of pre-OLTP ○ Clarify the definition of study day 1 in Section 5.3 • Table 5-1 updated to clarify the definition of the start date of Week 44 and baseline period • Table 5.6 updated to clarify the analysis visit window of HRU • Section 6.2 updated the definition of efficacy analysis set to include all endpoints • Section 7 updated to describe database disposition • Section 8.3 updated to clarify missing HRU dates imputation, missing items in eCOA,

Version Number	Date (DDMMYYYY)	Summary of Changes, including rationale for changes

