9.4 Demographic and Baseline Characteristics

Subject demographic and baseline characteristics will be summarized using descriptive statistics by randomized treatment group and overall study population using FAS. If multiple races have been reported for a subject, the subject will be categorized as multiple races.

At double-blinded baseline, following demographic and baseline characteristics will be summarized:

- Age (years)
- Sex
- Ethnicity
- Race
- Region (North America vs Others)
- Height (cm)
- Weight (kg)
- Body mass index (BMI, kg/m²)
- Targeted neurological disease diagnosis at baseline
- **Prior history of treatment with onabotulinumtoxinA**
- **Prior history of depression**
- Disease duration of migraine with or without aura
- **Disease duration of chronic migraine with or without aura**
- Age at onset of migraine
- Age at onset of chronic migraine
- **Prior migraine preventive treatment and reasons for discontinuation by medication category**
- **Concomitant oral migraine preventive treatment by medication category**
- **Number of prior migraine preventive treatment failures by medication category**
- Acute headache medication used during baseline period:
 - a) Migraine-specific
 - b) Non-migraine-specific
- Monthly migraine days during baseline period
- **Monthly migraine-free days during baseline period**
- Monthly headache days during baseline period

- Monthly **headache** days with **at least** moderate pain intensity during baseline period
- Monthly acute migraine-specific medication days during baseline period
- Monthly acute migraine-specific medication days during baseline period among baseline users
- Monthly acute headache medication days during baseline period
- **Monthly opioid/opioid-containing medication days (opioid-treated cohort only)**
- **Overuse of acute headache medication during the baseline period**
- Overuse of triptan during the baseline period
- Overuse of simple analgesics/NSAIDs during the baseline period
- Overuse of combination analgesics during the baseline period
- Overuse of combination therapies during the baseline period
- Monthly average **headache** pain intensity during baseline period
- **Monthly average MPFID physical impairment score during baseline period**
- **Monthly average MPFID overall impact on everyday activities score during baseline period**
- Beck Depression Inventory (BDI)-II total score severity grade
- Headache Impact Test (HIT-6) total score
- MFIQ impact on physical functioning

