9.7 Other Analyses

9.7.1 Analyses of Health Economic Endpoints

Health Resource Utilization Questionnaire (HRU)

The questionnaire is designed to collect data on HRU. Specifically, the aim is to capture frequency of **headache**-related hospitalizations and outpatient visits including emergency department visits, urgent care visits, and other clinical visits. The recall period for the HRU questionnaire is 24 weeks, and the HRU questionnaire will be administered on day 1, and week 24 of the DBTP. The questionnaire assessed at the early termination visit before week 24 should only include HRU recalled since the previous assessment at day 1 to avoid collecting duplicate information.

10. Changes From Protocol-specified Analyses

During the development of SAP amendment, it was realized that there are protocol-specified analyses that cannot be implemented/performed and the

protocol is not required to be amended. Ditans is included in the list of acute headache medications in Section 5.1. The definition of efficacy analysis set stated in the protocol is not applicable to all efficacy endpoints and has been corrected in Section 6.2 to what was intended. These changes will also be documented in the clinical study report.

11. Literature Citations / References

Quade, D. (1966), Rank analysis of covariance, University of North Carolina, Institute of Statistics Mimeo Series. No 483.

12. Data Not Covered by This Plan

There are no plans to specifically analyze or summarize the following data points.

- Data for biomarker development
- Data from the optional interview-based substudy

13. Appendices

Not applicable

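### SAP Amendment 1 counts ditans as acute headache medication but leaves them out of the Medication Overuse class list, so some mixed ditan users would be classed as non-overusers at baseline

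*SAP*

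**What the plan says.** SAP 5.1.1 lists the acute headache medications, and Amendment 1 adds "Ditan-based migraine medications" to that list. The version history describes the change as "Include ditans as acute migraine-specific medications and acute headache medication". SAP Section 10 declares it as a change from the protocol: "Ditans is included in the list of acute headache medications in Section 5.1".

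An acute headache medication day is "A calendar day (00:00 to 23:59) in which the subject takes ≥ 1 acute headache medication", so ditan days count. MOH is "Mean monthly AHMD ≥ 10 days AND mean MHD ≥ 14 days over 3 consecutive study months". The only class removed from it is gepants, by the words "excluding gepant-based medication in the derivation".

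The MO definition in SAP 5.1.1 has a combination criterion and several single-class criteria. The combination criterion is "≥ 10 days of a combination of ergotamines, triptans, opiates or opioid-containing meds or opioid combination-analgesic, non-opioid combination-analgesic medications or simple analgesics/NSAIDs", and it applies only when no single-class criterion is met. The single-class criteria are at least 10 days for opioids, triptans, ergotamines or non-opioid combination analgesics, and at least 15 days for simple analgesics/NSAIDs when nothing else is used in the month. Ditans appear nowhere in this definition, and it has no catch-all.

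MO is used in two places. The SAP 9.4 baseline table has the row "Overuse of acute headache medication during the baseline period" followed by four category rows. SAP 4.2 has four separate Yes/No overuse subgroups for the primary and secondary endpoints: triptan, simple analgesics/NSAIDs, combination analgesics and combination therapies.

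**The concern.** Amendment 1 carried ditans into acute headache medication, acute migraine-specific medication, headache day, qualified migraine headache and migraine day, but not into MO. The text marked as changed shows that the MO definition was itself edited in that amendment. Where the sponsor wanted a class left out, as with gepants in MOH, the SAP says so. It says nothing of the kind about ditans in MO.

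The result is that a ditan day counts as acute headache medication use but not toward overuse. For a subject who mixes ditans with another class, the same baseline table could show AHMD above 10 and overuse = No. Overuse at baseline is an entry condition (Protocol 6.3, criterion 108), so such a row would look like an eligibility failure when its cause is a definition gap. The combination-therapies subgroup would also place a mixed user in its No level.

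**Working it through.** The plan states no figure on this point, so there is none to reproduce. The check applies the written rules to illustrative months.

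Inputs, all from SAP 5.1.1: any acute headache medication, including a ditan, makes an AHMD; the MOH thresholds are AHMD ≥ 10 and monthly headache days (MHD) ≥ 14; the MO criteria are as described above.

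Assumptions: a complete 28-day diary, so the proration factor is 28/28 = 1; one drug class per day; MHD = 16; the combination-therapies flag is the first MO criterion; a combination means at least two listed classes. On the last assumption, if one class sufficed, 10 days of NSAIDs alone would qualify and the 15-day criterion would be redundant.

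Formulas: AHMD = all medication days. Combination count = days with a listed class. MO = Yes if a single-class criterion is met, or if the combination count is ≥ 10 with two or more listed classes.

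| Month | AHMD | Largest listed class | Combination count as written | MO as written | MO with ditans added to the combination list |
|---|---|---|---|---|---|
| 6 triptan + 5 ditan | 6 + 5 = 11 | 6 (< 10) | 6 (< 10) | No | Yes, 11 ≥ 10 |
| 6 triptan + 6 ditan | 12 | 6 (< 10) | 6 | No | Yes, 12 |
| 9 triptan + 9 ditan | 18 | 9 (< 10) | 9 | No | Yes, 18 |
| 8 simple analgesic + 6 ditan | 14 | 8 (< 15, not sole use) | 8 | No | Yes, 14 |
| 12 ditan | 12 | 0 | 0 | No | No, one class only |
| 6 triptan + 6 simple analgesic (control) | 12 | 6 | 12 | Yes | Yes |
| 12 triptan (control) | 12 | 12 (≥ 10) | not needed | Yes | Yes |
| 12 simple analgesic only | 12 | 12 (< 15) | one class only | No | No |

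Every month in the table reaches AHMD ≥ 10 with MHD 16, and the edit changes neither value. The four mixed ditan months move from No to Yes, and the other four rows do not change.

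The result depends on how far ditan days fall on separate days. In the first row one overlapping day leaves AHMD at 11 − 1 = 10, still at the threshold; two leave 9, below it.

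A second route follows from the sole-use condition. A subject with 16 NSAID days and 1 ditan day passes criterion 108 on the 15-day NSAID line. In the SAP, read literally, the one ditan day breaks sole use. The combination criterion then fails because only one listed class was used, so MO = No. With ditans in the list, the count is 16 + 1 = 17 days over two listed classes, and MO = Yes.

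**The case against.** The strongest reply is that eligibility keeps most of these subjects out. Criterion 108 admits overuse of combination treatment, short-acting opioids, triptans or ergots, and NSAIDs or simple analgesics. It does not name ditans, and neither do the protocol's overuse definitions in Appendix 1. This stands for ditan-only use: such a subject should be randomized only by deviation. It stands in part for mixed use, because a subject with 6 triptan and 5 ditan days enters only if ditans were read into combination treatment, a term the criterion leaves undefined. It does not cover the 16 NSAID + 1 ditan subject, who qualifies on NSAIDs alone.

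A reader might infer that the SAP contradicts itself whenever MOH thresholds are met and MO is No. The documents do not support that. MOH is a mean over three study months at a single AHMD threshold, while MO is tabulated on the baseline period with class-specific thresholds. The two can differ by design: sole use of simple analgesics on 10 to 14 days gives AHMD ≥ 10 and MO = No with no ditan involved.

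A reader might also take No on all four SAP 4.2 flags to mean a non-overuser. It does not. An ergotamine-only overuser is MO = Yes and still No on all four, because there is no ergotamine subgroup.

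Finally, the class list may have been left alone deliberately, to match the protocol's definitions. The documents do not settle this. If it was deliberate, the SAP still has to say so and state how mixed users are classified.

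**Conclusion.** The point holds for mixed ditan users. As written, the rule classes some of them as MO = No in the SAP 9.4 overall overuse row and as No for combination-therapies overuse in SAP 4.2 and 9.4. This rests on reading the class list as closed, which the wording supports, and on taking the combination-therapies flag from the first MO criterion.

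The number affected cannot be estimated and may be zero, because the documents give no rate of ditan use. Assuming that 1% to 3% of the 549 nonopioid subjects use ditans gives 549 × 0.01 ≈ 5 to 549 × 0.03 ≈ 16 users. That would count users rather than misclassified subjects, and the rate has no basis in the documents.

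It would be wrong to infer any effect on the main results. The primary endpoint uses AHMD and MHD, and neither the fixed-sequence testing nor the power calculation uses MO. The reach is the baseline overuse rows and one subgroup flag. The rule is wrong as written, and the matter is minor.

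**What to change.** In SAP 5.1.1, add ditans to the classes named in the combination criterion. Derive the SAP 9.4 overuse rows and the SAP 4.2 combination-therapies flag from the amended criterion, and record the change beside the existing ditan entry in SAP Section 10.

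Treat ditan-only use separately. Neither criterion 108 nor the protocol's overuse definitions give a ditan threshold, and a ditan-only criterion would change none of the four SAP 4.2 flags, because none of them is for ditans. Reconcile the MO definition with the acute headache medication list and state how such subjects are tabulated. If leaving ditans out of MO was intended, say so and state how both mixed and ditan-only users are shown.

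The cost is one phrase, one or two sentences and a code-list update. It needs no data beyond the acute medication use already recorded in the eDiary. The edit does not address sole use of simple analgesics on 10 to 14 days, which is a separate difference between AHMD and MO.
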